## **8.11          Medical resource utilization and health economics**

Not applicable.

# **9               STATISTICAL CONSIDERATIONS**

A description of statistical methods follows and will be described in more detail in the Statistical Analysis Plan (SAP).

## **9.1           Definition of analysis sets**

The Enrolled Set (ES) will consist of all study participants who signed the ICF.

The Randomized Set (RS) will consist of all randomized study participants.

The Full Analysis Set (FAS) will consist of all randomized study participants who received full or partial IMP according to the treatment the study participants actually received. The FAS will be used for summaries of demographics, medical history, prior and concomitant medications, IMP exposure, and general safety outcomes such as AEs, laboratory parameters, vital signs, and ECGs.

The PK Concentration Set (PKCS) will be a subset of the FAS, consisting of those study participants that received at least 1 dose of IMP and have at least 1 reported plasma concentration. All participants in the PKCS will be included in the listings. Participants with no protocol deviations to impact observed concentrations will be included in summary tables and figures of concentration-time profiles.

The PK Per-Protocol Set (PK-PPS) will be a subset of the FAS, consisting of those study participants who had no important protocol deviations affecting the PK variables and for whom a sufficient number of samples are available to determine at least 1 PK parameter. This analysis set will be used for all summaries and analyses of the PK parameters.

## **9.2 General statistical considerations**

All analyses will be performed using Statistical Analysis System® (SAS®) version 9.4 or later (SAS Institute, Cary, NC, USA).

For continuous variables, summary statistics will include number of study participants, mean, median, standard deviation (SD), minimum, and maximum. Categorical endpoints will be summarized using number of study participants, frequency, and percentages. Missing data will not be imputed.

If not otherwise stated, Baseline will be the last assessment prior to dosing. Measurement of specific Baseline values will be described in the SAP.

## **9.3 Planned efficacy/outcome analyses**

As efficacy is not evaluated in this study, there is no primary efficacy endpoint.

## **9.4 Planned outcome analyses**

### **9.4.1 Analysis of the primary endpoints**

The PK analyses will be performed on the PK-PPS.

The primary PK parameters ( $C_{max}$ ,  $AUC_{(0-t)}$ , and  $AUC$ ) will be evaluated according to a univariate model of analysis of variance (ANOVA). The model will include treatment group as a fixed effect. The dependent variables will be logarithmically transformed prior to statistical testing, following the usual recommendations. Natural logarithms (ln) will be employed. The 90% confidence interval (CI) of the adjusted geometric mean ratios will be calculated. Two independent comparisons will be made (ie, test 1 versus reference 1 and test 2 versus reference 2). For each of the respective comparisons, BE will be concluded if the 90% CIs for the ratio of the respective comparison are fully included in the acceptance range from 0.8 to 1.25 for  $AUC$ ,  $AUC_{(0-t)}$ , and  $C_{max}$ .

Sensitivity analyses may also be performed on the PK parameters.

### **9.4.2 Analysis of secondary PK parameters**

Additionally, a similar ANOVA will be also performed on log-transformed  $t_{1/2}$  to compare elimination characteristics between treatment groups (ie, test 1 versus reference 1 and test 2 versus reference 2).

The point estimate and the 90% CI for the median treatment differences for  $t_{max}$  will be computed according to the Hodges-Lehmann's method.

### **9.4.3 Study participant disposition and characteristics**

The number of study participants who were enrolled and randomized into the study, in each analysis set, and who completed or prematurely discontinued the study, as well as the reason for discontinuation, will be presented by treatment and overall using frequency counts and percentages. In addition, listings will be provided for study discontinuation, study participant disposition, and study participant analysis sets.

Study participant characteristics will include a summary and listing of the following:

- Demographics (including sex, age, race, ethnicity, height, weight, BMI, and lifestyle)
- Medical history
- Prior and concomitant medications

Concomitant medical procedures will only be listed.

## **9.5 Planned safety and immunogenicity analyses**

### **9.5.1 Safety analyses**

All safety parameters will be listed by study participant and treatment group using the FAS.

The incidence of treatment-emergent adverse events (TEAEs) will be determined by treatment group, where applicable. Absolute and relative frequencies for a given TEAE by preferred term as per the Medical Dictionary for Regulatory Activities (MedDRA®), as well as absolute and relative frequencies of individual TEAEs, will be determined within each treatment group and system organ class. Additional tables will summarize TEAEs by maximum event intensity and causal relationship with IMP per treatment group and overall. The actions taken for each TEAE, the time of onset of the TEAE after dosing, and the duration of each AE will be listed. The TEAEs leading to discontinuation and SAEs will also be summarized.

For continuous laboratory variables, values and changes from Baseline will be summarized at each time point. For categorized values according to the reference range, shift tables from Baseline to each postdose time point will be presented for selected variables. Values outside the reference range will be flagged in the data listings. The reference ranges will be reported.

Normal versus abnormal findings for the various ECG parameters and overall ECG will be analyzed as required, focusing on the identification of outliers and of any trends for changes following administration of IMP with respect to QT/QTcF. Descriptive statistics will be presented for ECG value and changes from Baseline over time.

Descriptive statistics will be reported for all vital sign measurements (including systolic and diastolic BP, pulse rate, and tympanic body temperature). Measured values and changes from Baseline will be summarized for all study participants by time point.

Abnormal findings in the physical examination will be presented in listings only.

### **9.5.2 Immunogenicity analyses**

Bimekizumab anti-drug antibody (ADAb) levels will be listed per study participant and summarized using summary tables and figures. The number (and percentage) of participants with

first occurrence of treatment-induced ADAb positivity will also be summarized at each postdose visit. The immunogenicity analyses will be further detailed in the SAP.

## **9.6 Handling of protocol deviations**

No protocol deviation is permitted, either in retrospect or prospect.

Important protocol deviations are identified as part of the data cleaning process in the Data Cleaning Plan (DCP). The objective of the data cleaning meeting will be to review and update (if necessary) the important protocol deviations in the DCP and discuss exclusion of study participants from analysis populations.

Furthermore, overall trends in protocol deviations will be discussed at the Data Evaluation Meeting. Through this data cleaning and evaluation process, all decisions regarding important protocol deviations and exclusions from analysis populations will be made. Protocol deviations (eg, missing assessments or visits) related to COVID-19 will be listed separately.

Accepted deviations from theoretical time points will be described in the appropriate documents and included in the trial master file (TMF).

After resolution of all issues, and documentation of all decisions, the database will be locked.

## **9.7 Handling of dropouts or missing data**

There will be no special procedures for handling missing data. All imputation of missing or partial dates for safety assessments, as well as handling values below the limit of quantification in the PK data, will be detailed in the SAP.

## **9.8 Planned interim analysis and data monitoring**

No formal interim analysis is planned for this study.

## **9.9 Determination of sample size**

This is a formal BE study to compare the PK of bimekizumab-SS-2mL (test 1) versus bimekizumab-SS-2x1mL (reference 1), and bimekizumab-AI-2mL (test 2) versus bimekizumab-AI-2x1mL (reference 2). Two independent comparisons will be made (ie, test 1 versus reference 1 and test 2 versus reference 2).

The between subject variability (CV%) observed in previous small studies following a single-dose administration of bimekizumab in healthy study participants (ie, UP0031, RA0124, UP0033, and UP0074) was 21% to 25% for AUC and 23% to 33% for  $C_{max}$ .

Assuming a geometric mean ratio of 0.9 between each pair of formulations and a between subject variability (CV%) of 33%, 93 study participants per group are required to assess BE (using an acceptance range of 0.8 to 1.25) with 80% power at the 5% significance level. In the event that the true mean ratio between each pair of formulations is 0.95, then with the same assumptions on variability and significance level there is >95% power to determine BE for that pair of formulations.

Sample size estimation was performed using SAS software (version 9.4).

Assuming a dropout rate and nonevaluable study participants of approximately 10%, 100 study participants per group for a total of 400 study participants are to be enrolled in the study. If this

10% rate is likely to be exceeded, due to unforeseen circumstances during the COVID-19 pandemic, then participants may be replaced.

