## Number of Study Participants

Assuming a dropout rate and nonevaluable study participants of approximately 10%, 100 study participants per group for a total of 400 study participants are to be enrolled in the study. If this 10% rate is likely to be exceeded, due to unforeseen circumstances during the coronavirus disease 2019 (COVID-19) pandemic, then participants may be replaced.

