### **6.3 Measures to minimize bias: randomization and blinding**

This is an open-label study.

A PAREXEL Biostatistician will write the randomization program and will provide a dummy output of the randomization for review in order to ensure compliance to study requirements.

Study participant treatment assignment will be random throughout the study. Study participants will be randomized in a 1:1:1:1 ratio to each treatment group as described in Section 4.1.

Copies of the randomization list will be sent before the start of the study to the following recipients:

- ClinBase™ setup designer

---

- Sponsor Drug Safety staff for SAE reporting
- Bioanalytical staff
- Site pharmacist and Pharmaceutical Services staff (for dispensing IMP)

Pharmacokinetic concentration data will not be available to the study team until after the last scheduled procedure for the last study participant in the study, so the decision to replace participants who dropped out or are missing PK visits due to COVID-19 can be made in an unbiased manner.

At the Screening Visit, each study participant will be assigned a unique 5-digit number from a range of numbers supplied by UCB. Once the Investigator determines that the study participant is eligible for the study, the study participant will be manually assigned to the next available randomization number by the Investigator or designee on the evening of Day -1. Each specific randomization number is tied to the treatment allocation on the randomization schedule, which can then be dispensed by the site pharmacist. This randomization number will also be recorded in the eCRF (ie, ClinBase; see Section 10.1.6).

The study design accounts for a 10% rate of dropouts and/or non-evaluable participants (participants with missing PK visits that are expected to impact derivation of  $C_{max}$  and/or AUC). The dropout rate will be closely monitored and if this 10% rate is likely to be exceeded, due to unforeseen circumstances during the COVID-19 pandemic, then participants may be replaced. The number of replacements will be discussed and agreed with the Sponsor. Replacement participants will be assigned the next available randomization number.

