## 2.4 Determination of sample size

This is a formal BE study to compare the PK of bimekizumab-SS-2mL (test 1) versus bimekizumab-SS-2x1mL (reference 1), and bimekizumab-AI-2mL (test 2) versus bimekizumab-

---

AI-2x1mL (reference 2). Two independent comparisons will be made (i.e., test 1 versus reference 1 and test 2 versus reference 2).

The between subject variability (CV%) observed in previous small studies following a single dose administration of bimekizumab in healthy study participants (i.e., UP0031, RA0124, UP0033, and UP0074) was 21% to 25% for AUC and 23% to 33% for Cmax.

Assuming a geometric mean ratio of 0.9 between each pair of formulations and a between subject variability (CV%) of 33%, 93 study participants per group are required to assess BE (using an acceptance range of 0.8 to 1.25) with 80% power at the 5% significance level. If the true mean ratio between each pair of formulations is 0.95, then with the same assumptions on variability and significance level there is >95% power to determine BE for that pair of formulations.

Sample size estimation was performed using SAS software (version 9.4).

Assuming a dropout rate and non-evaluable study participants of approximately 10%, 100 study participants per group for a total of 400 study participants are to be enrolled in the study. If this 10% rate is likely to be exceeded, due to unforeseen circumstances during the COVID-19 pandemic, then participants may be replaced.

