## 9.2 Statistical analysis of bioequivalence

### 9.2.1 Primary analysis

The primary PK parameters (AUC,  $AUC_{(0-t)}$  and  $C_{max}$ ) will be evaluated according to a univariate model of analysis of variance (ANOVA). The model will include treatment group as a fixed effect. The dependent variables will be logarithmically transformed by natural logarithms ( $\ln$ ) prior to analysis.

Two independent comparisons will be made:

- Test 1: Bimekizumab-SS-2mL versus Reference 1: Bimekizumab-SS-2x1mL
- Test 2: Bimekizumab-AI-2mL versus Reference 2: Bimekizumab-AI-2x1mL

For each comparison, the difference between the least squares means (LSM) will be estimated and back transformed in order to obtain the geometric mean ratio for the corresponding Test/Reference together with the 90% CI for the ratio.

For each of the respective comparisons, BE will be concluded if the 90% CIs for the ratio of the respective comparison are fully included in the acceptance range from 0.8 to 1.25 for AUC,  $AUC_{(0-t)}$  and  $C_{max}$ .

All participants in the PK-PPS will be included in the analysis as far as the data permit; a participant may be included in the analysis for one or more PK variables (i.e., if it was not possible to calculate AUC for a given participant, the participant may be included in the analysis of BE for  $AUC_{(0-t)}$  and  $C_{max}$ ).

The results of the BE analysis will be tabulated, for each comparison, including the geometric least squares means and 90% CI for treatment group, the estimated geometric mean ratio and 90% CI for the corresponding Test/Reference as well as the CV%.

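### 100 per group with 10% loss leaves 90 evaluable, not the 93 stated as required; 100 covers about 7% loss

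*Protocol*

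**What the plan says.** Protocol 9.9 assumes a true ratio of 0.9, a between-subject CV of 33%, an acceptance range of 0.8 to 1.25, 80% power and a 5% level, and concludes that "93 study participants per group are required to assess BE". It then goes from required to enrolled numbers: "Assuming a dropout rate and nonevaluable study participants of approximately 10%, 100 study participants per group", 400 in total. SAP 2.4 repeats both statements. The synopsis gives the 10% and the 100 per group but not the 93.

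Protocol 6.3 states the allowance without the word approximately: "The study design accounts for a 10% rate of dropouts and/or non-evaluable participants". It counts as non-evaluable anyone whose missing PK visits are expected to affect Cmax and/or AUC. The synopsis, Protocol 6.3 and 9.9, and SAP 2.4 all permit optional replacement on the same condition: "If this 10% rate is likely to be exceeded, due to unforeseen circumstances" of the pandemic.

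**The concern.** The required number, the enrolled number and the loss allowance cannot all be right together. If 93 are needed and 10% are lost, 100 is too few; if 100 are enrolled and 93 are needed, the design tolerates 7%.

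Two things follow. First, the sample-size justification of a formal bioequivalence study tells the reader that 10% loss is covered while 80% power is kept, and its own figures do not support that. Second, replacement was added to protect the sample size, but its condition is tied to 10%. A projected loss of 8%, 9% or 10% could leave fewer than 93 per group without meeting that condition.

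**Working it through.** **Inputs** (Protocol 9.9, repeated in SAP 2.4): ratio 0.9, CV 33%, limits 0.8 and 1.25, 80% power. The 90% confidence interval in Protocol 9.4.1 means two one-sided tests at 5% each. Allocation is 1:1:1:1 (Protocol 6.3).

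**Step 1: reproduce 93.**
- Log-scale SD: σ = √ln(1 + 0.33²) = √ln(1.1089) = 0.3215.
- Distance from the assumed ratio to the nearer limit: ln(0.9/0.8) = 0.1178.
- Normal approximation: n = 2σ²(1.645 + 0.842)²/0.1178² ≈ 92.1, so 93 per group.
- Exact power of the two one-sided tests, two-group degrees of freedom 2n − 2: 79.69% at 92 and 80.07% at 93.
- With the four-arm ANOVA degrees of freedom 4n − 4: 79.8% at 92 and 80.2% at 93.

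Either way, 93 is the smallest number that reaches 80%. The companion claim of more than 95% power at a ratio of 0.95 also reproduces (97.7% at 93).

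**Step 2: apply the loss.**
- 100 × (1 − 0.10) = 90, which is 3 short of 93.
- 93/(1 − 0.10) = 103.3, so 104 per group and 4 × 104 = 416 in total. The cruder 93 × 1.10 gives 103, also not 100.
- Largest loss that keeps 93 of 100: 1 − 93/100 = 7%.
- Overall: 400 × 0.90 = 360 evaluable, against 4 × 93 = 372.

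One hundred is what results from inflating 90, not 93: 90/0.90 = 100.

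**Step 3: the effect on power** (ratio 0.9, CV 33%, degrees of freedom 2n − 2).

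| Loss from 100 | n per group | Power |
|---|---|---|
| 7% | 93 | 80.1% |
| 8% | 92 | 79.7% |
| 9% | 91 | 79.3% |
| 10% | 90 | 78.9% |

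With four-arm degrees of freedom, power at 90 is 79.0%. The gap between 93 and 90 is 1.1 to 1.2 points.

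**Step 4: sensitivity at 90 per group.** At a ratio of 0.9, power is 85.0% for a CV of 30% and 94.0% for a CV of 25%; 80% is reached once the CV is about 32.5% or lower. At a ratio of 0.95 and a CV of 33%, power is 97.3%.

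**The case against.** The strongest reply is that 93 and 10% count different things. The 93 rests on a CV of 33%, the top of the range quoted for Cmax (23% to 33%). The 10% is a composite that includes participants who lack only an AUC. SAP 9.2.1 says that "a participant may be included in the analysis for one or more PK variables", so a participant without an AUC can still enter the Cmax analysis. If 3 of the 10 lost per group give a Cmax, that analysis has 93 and 80.1% power; if all 10 do, it has 100 and 82.6%. AUC, with a quoted CV of 21% to 25%, has ample power at 90 (94.0% at 25%).

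This stands as a caveat: 78.9% is the Cmax power only if none of the lost participants has a Cmax. It does not reconcile the figures. The documents do not say how the 10% divides and do not offer this reasoning for the 100. Protocol 6.3 applies the 10% to participants non-evaluable for either parameter, and bioequivalence requires all three parameters to pass.

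It is also fair that Protocol 9.9 says approximately, that dropout is monitored, and that replacement is prospective. But Protocol 6.3 drops the hedge, and replacement is optional and limited to pandemic circumstances. These points limit the harm without making the numbers agree.

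**Conclusion.** The point holds. The 93 is correct under the stated assumptions; the claim that 100 per group absorbs 10% loss is not, because the figures support 7%. The shortfall is 3 per group, or 12 evaluable participants overall. It costs about one point of power per comparison at the conservative ratio and CV, if lost participants contribute no Cmax. The more-than-95% statement survives, and no analysis set, model or decision rule is affected. This is a definite inconsistency in a core design statement with a modest consequence, and it should be corrected.

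**What to change.** Make the three figures agree in Protocol 9.9 and SAP 2.4, and align the matching sentences in the synopsis and Protocol 6.3. Either of these would do:

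- *One hundred per group allows for about 7% dropouts and non-evaluable participants while keeping 93 per group.*
- *With 10% loss, about 90 per group remain. If none of those lost contributes a Cmax, power is about 79% at a ratio of 0.9 and a CV of 33%, and about 97% at a ratio of 0.95.*

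If the sponsor chose 100 because some non-evaluable participants were expected to yield a Cmax, that expectation and the assumed split should be written down instead.

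The cost is wording in two documents, with whatever ethics committee review a minor protocol change requires, and a slightly less favourable stated figure. No extra participants and no change to the analysis are needed. Raising enrolment to 416, or replacing participants at a lower loss rate, would dose additional healthy volunteers for about one point of power. Replacements also take the next randomization number ("Replacement participants will be assigned the next available randomization number"), so they could not be directed to the group that is short. Neither step is needed to correct the inconsistency.

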## **10 SUPPORTING DOCUMENTATION AND OPERATIONAL CONSIDERATIONS**

### **10.1 Appendix 1: Regulatory, ethical, and study oversight considerations**

#### **10.1.1 Regulatory and ethical considerations**

The study will be conducted under the auspices of an IEC, as defined in local regulations, International Council for Harmonisation (ICH)-GCP, and in accordance with the ethical principles that have their origin in the Declaration of Helsinki.

The Investigator/UCB will ensure that an appropriately constituted IEC that complies with the requirements of the current ICH-GCP version or applicable country-specific regulations will be responsible for the initial and continuing review and approval of the clinical study. Prior to initiation of the study, the Investigator/UCB will forward copies of the protocol, ICF, IB, Investigator's curriculum vitae (if applicable), advertisement (if applicable), and all other study participant-related documents to be used for the study to the IEC for its review and approval.

Before initiating a study, the Investigator will have written and dated full approval from the responsible IEC for the protocol.

The Investigator will also promptly report to the IEC all changes in the study, all unanticipated problems involving risks to study participants or others, and any protocol deviations, to eliminate immediate hazards to study participants.

The Investigator will not make any changes in the study or study conduct without IEC approval, except where necessary to eliminate apparent immediate hazards to the study participants. For minor changes to a previously approved protocol during the period covered by the original approval, it may be possible for the Investigator to obtain an expedited review by the IEC as allowed.

As part of the IEC requirements for continuing review of approved studies, the Investigator will be responsible for submitting periodic progress reports to the IEC (based on IEC requirements), at intervals appropriate to the degree of study participant risk involved, but no less than once per year. The Investigator should provide a final report to the IEC following study completion.

UCB (or its representative) will communicate safety information to the appropriate regulatory authorities and all active Investigators in accordance with applicable regulatory requirements. The appropriate IEC will also be informed by the Investigator or the Sponsor, as specified by the applicable regulatory requirements in each concerned country. Where applicable, Investigators are to provide the Sponsor (or its representative) with evidence of any such IEC notification.

